9.0 TREATMENT/INTERVENTION PLAN

9.1 Dosing Instructions and Schedule

9.1.1 Avelumab Dosing Instructions and Schedule

One cycle of avelumab is defined as two weeks. Administration of avelumab will commence after completion of pre-treatment procedures. Patients will receive avelumab 10mg/kg as an IV infusion Q2W. In order to mitigate infusion related reactions, a premedication with an antihistamine and with acetaminophen 30 to 60 minutes prior to each dose of avelumab is mandatory (for example, 25-50 mg diphenhydramine and 500- 650 mg acetaminophen IV or oral). The treating oncologist may use equivalent or similar medications as available at their discretion.

Two cycles will be given before starting radiation therapy. After 2 cycles of avelumab, a short course of SBRT (after the end of Cycle 2 and before Cycle 3, Day 1) will be delivered to a portion of MPM that is symptomatic or at risk of causing symptoms. Avelumab treatment continues during and after RT for up to two years or until disease progression. Avelumab may be continued after disease progression at the discretion of the investigator if criteria in section 4.2 are met.

The first day of dosing is considered Day 1 of the cycle. Day 1 of Cycle 1 is considered the date of first dose and is used to determine the maximum 24 months of treatment. Trial treatment should be administered on Day 1 of each cycle. Trial treatment may be administered up to 3 days before or after the scheduled Day 1 of each cycle due to administrative reasons. All trial treatments will be administered on an outpatient basis.

9.1.2 SBRT Dosing Instructions and Schedule

SBRT will be administered after 2 cycles of avelumab are complete, with fractionation and schedule at the discretion of the treating radiation oncologist. The radiation dose and organ dose constraints will be in accordance with standard institutional guidelines (see appendix 1). Avelumab and SBRT should not be delivered on the same day. SBRT may be delayed up to 6 weeks for immunotherapy toxicity management. If the patient is unable to receive radiation within the 6 weeks, they will be removed from protocol and replaced.

Patients will be treated on an outpatient basis. Patients will be evaluated by the radiation oncology team and then undergo simulation for 3D-CRT, IMRT, or VMAT, the choice of which is determined by the radiation oncologist.

Each patient will be positioned in a custom immobilization and undergo a CT scan (slice spacing 2-2.5 mm, depending on the scanner) for treatment planning.

The radiation oncologist will delineate the gross tumor volume (GTV) on the planning scan. If clinically indicated for lesions within the chest, only, the 4D-CT scan will be used to account for respiratory motion.

Target volumes: The definitions of volumes will be in accordance with the 1999 ICRU report #62.

Definition of the gross tumor volume (GTV):

The volume determined to clinically correspond with the area requiring palliation will constitute the GTV.

Definition of the internal target volume (ITV):

For patients who undergo 4DCT simulation, only: an ITV will be created based on the 4D-CT scan to account for all respiratory motion throughout the respiratory cycle, thus resulting in a motion-inclusive ITV.

Definition of the clinical target volume (CTV):

The CTV will be defined as the ITV plus typically 0.2cm to account for microscopic tumor extension.

Definition of the planning target volume (PTV):

The PTV will include the CTV plus a margin of 0.5 cm to account for setup uncertainties.

Critical normal tissues in proximity to the irradiated lesion will be contoured.

Hypofractionated guidelines based on current MSKCC guidelines will be applied (see appendix 1).

Isocenter is at the center of the GTV. Treatment is delivered with 6 or 15 MV photon beams. IMRT/VMAT will use the dynamic multileaf collimator (DMLC or sliding window) technique, on a Varian LINAC. The IMRT optimization algorithm uses an iterative gradient search method to minimize a quadratic objective function that can include terms to impose target dose uniformity, limit normal tissue maximum and mean doses and impose dose-volume constraints. Calculations are performed on a commercial treatment planning system using the analytic anisotropic algorithm (AAA) or Acuros algorithm (Varian Eclipse™).

Radiation will be given outpatient Monday to Friday, excluding holidays, until all (≤ 8) treatments have been completed. If the patient misses a scheduled treatment, this treatment will be added on the end of the initial treatment plan. Each treatment day, the patient will be positioned supine on the treatment table with custom immobilization. Patients are first positioned with the use of skin tattoos and an in-room laser localization system. Patients will then undergo a cone-beam CT prior to each fraction. Refinements in patient positioning are made based on the on-board 3D imaging. Patients will be matched based on the tumor within a 2mm tolerance, which will be approved by the attending radiation oncologist. The radiation treatment will then be administered. All patients will be monitored for gross body movement using intra-fraction motion such as infrared, Align RT or interval KV bone match.

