1.0 PROTOCOL SUMMARY AND/OR SCHEMA

Study Title	A Safety Study of Avelumab plus SBRT in Malignant Mesothelioma (MPM)
Investigational drug	Avelumab
Study Centers	MSKCC Main Campus and Regional Sites
Study Objectives	To evaluate the efficacy and safety (defined as the incidence of any grade 3+ non-hematologic toxicity) of combining SBRT and avelumab for the treatment of MPM
Study Endpoints	
Primary Endpoint
 
Safety of avelumab + SBRT: rate of grade 3 or higher non- hematologic toxicity (CTCAE v4.0) 
Secondary Endpoint
 
Overall response rate defined by modified RECIST 1.1 for mesotheliomaResponse of irradiated (in-field) and unirradiated (out-of-field) lesions as defined by RECIST 1.1Progression-free and overall survival 
Exploratory Objectives
 
T-cell infiltration both in- and outside the irradiated fieldSerum immune phenotype at baseline and after avelumab + SBRTConcordance of imaging using diffusion-weighted and DCE-MRI, and PET with biopsy sample results
Patient Population	Patients with a histologically/cytologically proven malignant pleural or peritoneal mesothelioma who have received one or more lines of standard treatment.
Number of Patients	27 patients maximum 13 patients will be recruited for Stage 1. If requirements for expansion are met, another 14 patients will be recruited for Stage 2.
Inclusion Criteria (summarized)	
Patient willing and able to provide written informed consent for the trial.Patient age \geq 18 at time of consent.Unresectable or stage IV malignant pleural or peritoneal mesothelioma (MPM).Histological and/or cytological confirmation of MPM.At least one prior therapyAt least one targetable lesion appropriate for palliative SBRT.Karnofsky Performance Score (KPS) \geq 70%Adequate organ function, defined below in Section 6.1

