2.1 OBJECTIVES AND SCIENTIFIC AIMS

- The primary objective of this study is to evaluate the safety of avelumab plus SBRT. This study is designed to include both pleural and peritoneal mesothelioma.
- The secondary objectives are to assess:
 - Overall response rate (ORR) using modified RECIST for mesothelioma treated with SBRT and avelumab.
 - Response of irradiated (in-field) and unirradiated (out-of-field) lesions defined by RECIST 1.1 for extrathoracic disease
 - Progression-free and overall survival
- Exploratory objectives are to evaluate T-cell infiltration and phenotype both in- and outside the irradiated field, serum immune phenotype before and after avelumab plus SBRT, and correlate imaging response (DW/DCE-MRI and PET) with biopsy sample results.

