4.3 Intervention

The main objective is to evaluate the safety of a novel combination of avelumab (anti-PD-L1 mAb) and stereotactic body radiation therapy (SBRT) for end-stage malignant pleural and peritoneal mesothelioma (MPM).

The safety endpoint of the trial will be assessed based on grade 3 or higher non-hematologic toxicity.

One cycle of avelumab is defined as two weeks. The treatment will consist of one dose of avelumab every other week (Q2W) as well as a short course of SBRT after the first two doses of avelumab. Patients will receive avelumab 10mg/kg as an IV infusion every 2 weeks. Avelumab will be continued up to 24 months or until disease progression. Patients may continue Avelumab after RECIST-defined radiologic progression of disease if the following criteria are met: absence of clinical symptoms or signs indicating clinically significant disease progression; no decline in performance status; absence of rapid disease progression or threat to vital organs or critical anatomical sites [e.g., CNS metastasis, respiratory failure due to tumor compression, spinal cord compression]

requiring urgent alternative medical intervention; no significant, unacceptable or irreversible toxicities related to study treatment.

Patients will be treated with SBRT according to standard image-guided radiation treatment procedures. Patients will have a CT simulation (including 4DCT scanning if clinically indicated) with 2mm slice thickness and daily cone-beam CT verification of patient setup and tumor position. Patients will be treated in ≤ 8 fractions.

To further enhance our current understanding of tumor immunology as well as prognostic biomarkers, we will collect peripheral serum samples before, during and after treatment, and tumor biopsies.

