13.1 CRITERIA FOR REMOVAL FROM STUDY

Patients should **permanently** discontinue treatment with avelumab for the reasons enumerated in Section 9 or in the event of:

- Intolerable adverse events (e.g. CTCAE v4.0 grade 3 or 4) that cannot be managed by dose modification or delay
- Further dose modification or delay considered necessary but not allowed per protocol section 9.4
- Pregnancy¹
- Withdrawal of informed consent²
- If the treating physician determines that it is in the best interest of the patient to stop study drug
- Non-compliance with the defined treatment plan

Patients will be removed from study after treatment ends in the event of:

- Death
- Pregnancy¹
- Withdrawal of informed consent²
- Non-compliance with the defined follow up studies

¹Pregnancy: In case of a patient or the patient's partner becoming pregnant during the trial the investigational drug has to be immediately stopped and the patients must be followed-up until birth or other termination of the pregnancy. Repeat counseling on birth defect risk must be offered.

²Consent withdrawal: in case a patient withdraws his/her consent for taking drug, it is of utmost importance for the robustness and integrity of the trial results that his/her safety data are recorded until the end of the 52 weeks period. Thus, all patients will be asked to follow their visit schedule until 52 weeks.

Patients who discontinue from this trial are not allowed to be reenrolled in this trial. Patients who discontinue medication within the first two weeks (during the washout period) will be replaced. For the patients who stopped trial before enrollment, their data will be part of the description of the screening population.

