14.0 BIOSTATISTICS

The primary endpoint, the safety of a combination of avelumab and SBRT, will be defined based on the rate of any grade 3 or higher non-hematologic toxicity within the first 3 months after SBRT (for the rest of the section this will be referred to as AE). A two-stage stopping rule will be used to protect patients' safety. If 3 or more among the first 13 patients develop AEs, then the trial will be stopped and declared unsafe. Otherwise, an additional 14 patients will be enrolled and treated. If, among the total 27 patients, 5 or more patients are observed to have AEs, then the trial will also be declared unsafe. This stopping rule has a power of 80% declaring the true AE rate of 0.1 or lower safe, and a type 1 error rate (alpha) of 5% declaring true AE rate of 0.3 or higher safe.

For secondary endpoints, the overall response and the irradiated lesion and non-irradiated lesion response rates (4 months from start date of the combined therapy) based on RECIST 1.1 response criteria will be summarized by sample proportions and their confidence intervals. PFS and OS will be evaluated by Kaplan-Meier method.

For the exploratory objectives, we will evaluate changes of T-cell infiltration and serum immunophenotype at baseline and after SBRT + immunotherapy both in- and outside the irradiated field. The former is measured as numerical values so we will use Wilcoxon signed-rank test. The latter is categorical so we will tabulate it and employ the marginal homogeneity test. Due to the expected small sample size, results will be interpreted cautiously. The imaging studies using DWI-MRI and DCE-MRI, and FDG-PET will be correlated with biopsy results by McNemar's tests.

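### Severe avelumab lead-in toxicity that prevents SBRT leads to replacement, so it cannot count toward the 3/13 and 5/27 safety rule

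*Combined protocol and SAP*

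**What the plan says.** Section 14 defines the primary event as the "rate of any grade 3 or higher non-hematologic toxicity within the first 3 months after SBRT" and uses that meaning for both boundaries: stop at 3 or more events among the first 13 patients, and declare unsafe at 5 or more among 27. It gives 80% power at a true rate of 0.1 and a 5% error at 0.3.

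The window opens after an avelumab lead-in. Section 9.1.1: "Two cycles will be given before starting radiation therapy". At two weeks per cycle this is about 4 weeks, and the Section 10.1 calendar puts SBRT near day 29. Section 9.1.2 adds "SBRT may be delayed up to 6 weeks for immunotherapy toxicity management" and then "If the patient is unable to receive radiation within the 6 weeks, they will be removed from protocol and replaced". Section 13.1 has a second replacement rule: "Patients who discontinue medication within the first two weeks (during the washout period) will be replaced". The schedule contains no washout, so that phrase does not narrow the rule.

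The objective is stated without a window. Section 2.1: "The primary objective of this study is to evaluate the safety of avelumab plus SBRT". The summary ("Safety of avelumab + SBRT: rate of grade 3 or higher non- hematologic toxicity") and Section 4.3 ("The safety endpoint of the trial will be assessed based on grade 3 or higher non-hematologic toxicity") are equally general.

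**The concern.** In a safety trial, the reason a patient drops out of the count should not be the outcome being counted. Section 9.1.2 names immunotherapy toxicity as the reason for delaying SBRT and then replaces the patient if the delay runs out. Section 9.4.1 makes the route concrete: grade 3 and grade 4 drug reactions end avelumab, apart from listed exceptions, and a stop in the first two weeks leads to replacement under Section 13.1. A patient who is never irradiated has no SBRT date and so no window in which to have an event. Section 14 has no clause that brings replaced patients back.

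The trial asks whether giving avelumab and then SBRT is safe. A patient too ill from the first component to receive the second bears on that question. Read literally, three patients who never reach SBRT because of grade 4 lead-in toxicity would add nothing to the stage 1 count.

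**Working it through.** **Inputs.** From Section 14: 13 patients then 14 more; continue with at most 2 events; safe with at most 4 of 27; rates 0.10 and 0.30. From Section 3.2 (avelumab alone, 53 patients): 7.5% with grade 3+ related events, median follow-up 46 weeks, median PFS 17.1 weeks. Lead-in of 4 weeks from Section 9.1.1. The share q of patients replaced for severe lead-in toxicity is not in the documents and is assumed.

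**1. The plan's own figures.** P(safe | p) = Σ over x = 0, 1, 2 of P[Bin(13,p) = x] × P[Bin(14,p) ≤ 4 − x].

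- p = 0.10: 0.2542×0.9908 + 0.3672×0.9559 + 0.2448×0.8416 = 0.2518 + 0.3510 + 0.2060 = 0.8088.
- p = 0.30: 0.00969×0.5842 + 0.05398×0.3552 + 0.13881×0.1608 = 0.0057 + 0.0192 + 0.0223 = 0.0472. Stage 1 stops with probability 0.7975.

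Both agree with the stated 80% and 5%.

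**2. Direction.** Let T be the overall rate of grade 3+ non-hematologic toxicity from first dose through 3 months after SBRT. If a share q is replaced, the rate that the rule sees is (T − q)/(1 − q), which is never above T. Replacement can only lower the counted rate.

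**3. An illustrative range for q.** Spreading 7.5% evenly over 46 weeks gives 0.075 × 4/46 = 0.65%; over 17.1 weeks, 0.075 × 4/17.1 = 1.75%. This treats every lead-in event as preventing SBRT. The 7.5% includes decreased lymphocytes and covers only related events, so the true figure could be lower or higher.

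**4. Effect at T = 0.30.**

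| q | Counted rate | P(declared safe) | Stage 1 stop |
|---|---|---|---|
| 0 | 0.3000 | 4.7% | 79.8% |
| 0.65% | 0.2954 | 5.2% | 78.7% |
| 1.75% | 0.2875 | 6.2% | 76.9% |
| 2.5% | 0.2821 | 6.9% | 75.6% |
| 5% | 0.2632 | 10.1% | 70.6% |

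The last two rows are less plausible: q = 5% would put two thirds of the 7.5% into the first four weeks. The 5% level is passed at q of about 0.38%, mainly because the exact error already stands at 4.7%.

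**5. Power if such patients are counted, boundaries unchanged, post-SBRT rate 10%.** If every lead-in event prevents SBRT, the counted rate is q + (1 − q)×0.10 = 0.1059 or 0.1158 for q = 0.65% or 1.75%, and P(declared safe) is 78.1% or 73.0%. If half do, the rate is q/2 + (1 − q/2)×0.10 = 0.1029 or 0.1079, giving 79.5% or 77.1%. Part of this fall is the rule responding to an overall rate above 10%.

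**6. Bias from replacing only event-free patients.** Suppose q = 1.75% and a share m misses SBRT without toxicity (assumed). With r = (1 − q)(1 − m), the counted rate is (q + 0.10r)/(q + r). For m = 10%, r = 0.8843 and the rate is 11.7%; for m = 20%, r = 0.7860 and the rate is 12.0%. Without such losses it is 11.6%.

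**The case against.** Section 14 states the window openly. No combination has been delivered before SBRT, avelumab alone already has data in 53 mesothelioma patients, and replacing patients who never receive the combination is common. Section 11.1 reports the most common avelumab events as all grade 1 or 2. Three or more lead-in cases among 13 would be very rare: about 0.008% at q = 0.65% and 0.14% at q = 1.75% (binomial). Lead-in events are recorded from first dose (Section 11.1.1), reported when serious (Section 17.3) and overseen by the monitoring committee (Section 16.3).

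Most of this stands. The post-SBRT window is defensible, and the size is small. What it does not justify is removing a patient from the count because of severe toxicity. None of those oversight routes feeds the 3/13 and 5/27 rule or the declared conclusion.

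Three stronger readings are tempting and not supported:

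- A reader might infer that the stated 80% and 5% are wrong. They are right for the event as defined, in irradiated patients.
- A reader might infer that severe lead-in toxicity goes unmonitored. It does not; it is only outside the formal rule.
- A reader might infer from the unwindowed objectives that counting must start at the first dose for everyone. Objectives often leave the window to the statistics section. Avelumab may run to 24 months, so a window from first dose to 3 months after SBRT would not cover all treatment either. Moving the start is an optional design choice.

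**Conclusion.** The gap is real and narrow. Under Sections 9.1.2, 13.1 and 14 as written, a patient whose grade 3+ non-hematologic lead-in toxicity prevents SBRT is replaced and cannot count toward either boundary. This replacement depends on the outcome and always works toward a finding of safety.

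Confidence in the textual gap is high. Its size rests on the assumed q: in the illustrated range the false-safe probability at a 30% overall rate moves from 4.7% to between 5.2% and 6.2%. It should be fixed because it biases a safety stopping rule and the remedy is cheap, not because the likely error is large.

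A lead-in event that resolves before SBRT in a patient who is then irradiated is a different case. It falls outside a legitimately chosen window and needs reporting only. The text does not settle whether an event that persists into the window counts.

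**What to change.** - In Sections 9.1.2, 13.1 and 14, state that a patient who has grade 3+ non-hematologic toxicity after the first avelumab dose, and for that reason does not receive SBRT, counts as an event within the 13 or 27. State that only patients who miss SBRT without such toxicity are replaced. Record the reason for each missed SBRT so that the rule can be applied.
- Keep the post-SBRT window for irradiated patients and keep both boundaries.
- Beside the primary result, report lead-in grade 3+ events in irradiated patients and all replacements with reasons.
- Reconcile removal from protocol in Section 9.1.2 with the safety follow-up to 90 days after last avelumab in Section 11.2, so that patients who are never irradiated are still followed.

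**Cost.** An amendment to three sections. No new data collection is needed, since adverse events are already recorded from first dose. At a 10% post-SBRT rate, power falls from 80.9% to at worst 78.1% (q = 0.65%) or 73.0% (q = 1.75%), and to 79.5% or 77.1% if only half of lead-in events prevent SBRT. Replacing only event-free patients adds the slight upward bias shown in step 6. The clinical rules for delay and discontinuation are unchanged.

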9.2 Monitoring of Dose Administration

Subjects will be monitored during avelumab administration and for a minimum of 2 hours after infusion with assessment of vital signs. Subjects will be monitored during avelumab administration and for a minimum of 30 minutes after infusion with assessment of vital signs if there are no infusion related reactions within the first 8 cycles. As with any antibody, allergic reactions to dose administration are possible. Appropriate drugs and medical equipment to treat acute anaphylactic reactions must be immediately available, and study personnel must be trained to recognize and treat anaphylaxis. The study site must have immediate access to

emergency resuscitation teams and equipment in addition to the ability to admit subjects to an intensive care unit if necessary.

Avelumab should be administered in a setting that allows for immediate access to an intensive care unit or equivalent environment and administration of therapy for anaphylaxis, such as the ability to implement immediate resuscitation measures. Steroids (dexamethasone 10 mg), epinephrine (1:1,000 dilution), allergy medications (IV antihistamines), bronchodilators, or equivalents at the treating oncologist's discretion, and oxygen should be available for immediate access.

9.3 Concomitant Medications

9.3.1 Permitted Concomitant Medications

Investigators may prescribe concomitant medications or treatments (e.g., acetaminophen, diphenhydramine) deemed necessary to provide adequate prophylactic or supportive care except for those medications identified as "excluded" as listed in Section 9.3.2.

9.3.2 Excluded Concomitant Medications

Subjects must be instructed not to take any medications, including over-the-counter products, without first consulting with the investigator.

The following medications are considered exclusionary during the study. The Principal Investigator must be notified if a subject receives any of these during the study.

- Any investigational anticancer therapy.
- Any concurrent chemotherapy, immunotherapy, or biologic therapy. Concurrent use of hormones for non-cancer-related conditions (e.g., insulin for diabetes and hormone replacement therapy) is acceptable.
- Immunosuppressive medications including, but not limited to systemic corticosteroids (>10 mg/day prednisone or equivalent), methotrexate, azathioprine, and tumor necrosis factor alpha (TNF- α) blockers. Use of immunosuppressive medications for the management of investigational product-related AEs, in subjects with contrast allergies is acceptable. In addition, use of inhaled and intranasal corticosteroids is permitted.

